Protocol for a study to investigate the prevalence and nature of respectful maternity care during institution delivery in Gombe State, Nigeria and to improve measurement methods for respectful care

Investigators

[name] (Research Fellow, ITD, DCD/ IDEAS Project Country Coordinator, Nigeria) [name] (Associate Professor, ITD, DCD)

IDEAS Project
Informed Decisions for Actions to Improve Maternal and Newborn Health
London School of Hygiene & Tropical Medicine

Abbreviations and acronyms

ANC Antenatal Care

BMGF Bill and Melinda Gates Foundation

HFW Health Facility Workers

LGA Local Government Authority

MNCH Maternal Newborn and Child Health

MDGs Millennium Development Goals

PHC Primary Health Care

RMC Respectful Maternal Care

SDGs Sustainable Development Goals

SAQIP Social Accountability and Quality Improvement Project

SPHCDA State Primary Health Care Development Agency

SBA Skilled Birth Attendant

WHO World Health Organization

1 Background

Reducing the deaths of women during pregnancy, childbirth or within forty-two days of termination of pregnancy from causes related to the pregnancy or its management remains a global priority, and a major challenge to the Nigerian health systems.^{1,2} Pregnancy related outcomes nationally are far from the acceptable levels enshrined in the past Millennium Development Goals (MDGs) and the current Sustainable Development Goals (SDGs). Worst still, are maternal mortality and morbidity indices in the Northeastern Nigerian states consisting of Adamawa, Bauchi, Gombe, Maiduguri, Taraba and Yobe states, which remained alarmingly poor in comparison to other Nigerian states.²

To address this challenge, substantial investments have been made and multiple strategies have been implemented in the past, driven by national institutions or international organisations, aimed at improving institutional deliveries with skilled assistance, an evidence based lifesaving intervention, though they have had limited success.³ Increases in the proportion of women delivering at health facilities have been marginal in Nigeria. In more than a decade, institutional delivery only increased by a 3-percentage point: 33% (in NHDS 2003), 35% (in NDHS 2008) and 36% (in NDHS 2013).^{2,4} In a recent household survey in Gombe state, more than 60% of women delivered at home in 2016.¹

Several reasons have been put forward to account for the low institutional delivery in Gombe state which includes women's preference to deliver at home due to cultural or religious beliefs, costs, geographical access and poor perception of the quality of available services at the health facilities including absence of essential medicines and staff, and attitude of health workers.^{3,5} Disrespectful treatment from health care providers is increasingly seen as one of the leading reasons behind the low utilisation of maternal and newborn health services in settings with poor MNH outcomes, sometimes even more powerful a deterrent to facility delivery than the more commonly recognized deterrents such as geographic and financial barriers.^{6,7}

Although, despite the wide acknowledgement of this behaviour by policy makers, program staff and community members, there is no empirical evidence to support the prevalence of disrespect & abuse in Gombe state. Further, there is limited understanding as to what constitute respectful maternal care (RMC) in this context, with the discourse mainly driven by findings in other countries or settings.

Studies on attitudes of health care workers towards women during pregnancy and childbirth conducted in Ethiopia, Kenya and Tanzania discovered that disrespectful and abusive behaviour at the health facilities was more prevalent than earlier thought, and that this was an important factor to influence women's decision to deliver in a health facility or not.⁸⁻¹⁰

¹ IDEAS household survey Gombe state 2016

1.1 Rational

To improve the survival of mother and their newborns, the Bill & Melinda Gates foundation has been funding a number innovations to generate demand and improve supply of MNH services through implementation grantees in Gombe state since 2009. Findings from three IDEAS surveys in Gombe state in 2012, 2015 and 2016 highlighted the need to do more, before desirable maternal and newborn health outcomes can be achieved in Gombe state. While some improvements were observed for example, increases in delayed bathing for both home and facility births, increases in clean cord care and immediate initiation of breastfeeding for facility births, and increases in hand washing with soap for home births,⁴ there was no evidence of improvement in the frequency of interactions between 2012 to 2015 across the continuum of care.⁴ Similarly, maternal PNC, newborn PNC and skilled attendant at birth remained low in 2016.¹

These findings led to the review and refinement of the strategies (to improve MNH outcomes) being implemented in Gombe. On the demand side, a Village Health Worker scheme has now replaced the use of 'Traditional Birth Attendants (TBAs)' and 'women volunteers' to reach mothers and newborns at home with the aim of promoting the uptake of antenatal care and facility delivery, promoting the uptake of life-saving behaviours at home, identification of pregnant women with danger signs and referring them to health facilities for extra care. On the supply side, the new strategy is focused on improving the health systems' responsiveness and quality of health services including provision of supplies and essential medicines, clinical training, and improving respectful maternity care among others.

1.2 Overview of this study

The IDEAS project is part of this wide partnership with GSPHCDA, Pact, SFH, C4C and E4A working on MNH in Gombe, as a measurement, learning and evaluation (MLE) grant. IDEAS project aims to improve the health and survival of mothers and babies through generating evidence to inform policy and practice. In line with IDEAS project's overarching aim, the study described here will generate empirical evidence on the quality of MNH care as it relates to the frequency and nature of RMC during institutional delivery in Gombe state, to inform state-level and global actions to better promote RMC, and to improve measurement methods for RMC. The study will aim to answer the following the research questions:

Q 1 What is the prevalence of respectful maternity care during institutional delivery in Gombe State? (Objective 1)

To be determined in two ways: 1) prevalence of respectful maternity care based on how frequently mothers regarded the interaction with health workers or health facility conditions

during their last institutional delivery to be respectful, through household surveys of mothers with births in the 24 months prior to interview; 2) prevalence of RMC based on how frequently the interactions with health workers or facility conditions during institutional delivery are deem (by general consensus) to be humiliating or undignified, through observation of births (in line with submission by Freedman et al¹¹).

Q 2 What is the validity of self-reported measures of respectful maternity care?

To be determined by comparing observable respectful maternity care behaviors documented during observation of births as gold standard measures of RMC, compared to reported occurrence of RMC during exit interview with observed women on discharge from facility and again during household-follow interview with observed women 6-12 months after birth to test the validity of self-reporting i.e. do women report their experience of RMC consistently, and extent of normalization of RMC i.e. the extent to which some aspect of RMC are normalized in Gombe.

Q 3 What utilities do women attach to dimensions of respectful maternity care during institutional delivery in Gombe State?

To be determined using choice experiments to explore women's preferences for interactions with birth attendants (e.g. competency, friendliness...) and conditions of place of delivery (e.g. availability of equipment, cleanliness...) during institutional delivery, integrated within the household follow-up interviews (6-12 month post-delivery) and supported by qualitative interviews.

In combination, these different measurement approaches respond to the global call for more attention and effort around defining, improving, and accurately measuring RMC.¹¹⁻¹³ As the study is nested within IDEAS annual household surveys and 6-monthly facility surveys, changes in frequency or prevalence of these dimensions of RMC can be tracked or observed over more than one measurement period. Engagement – discussions and evidence sharing – with other stakeholders working on RMC in Nigeria such as white Ribbon Alliance, USAID and UKaid is expected.

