4.2 Study implementation

The study will be conducted in three phases 1) formative, 2) data collection and 3) data analysis, synthesis and dissemination phases:

Formative phase – a formative research will be carried out to identify an appropriate tool, generate additional items, adapt and translate the tool into Hausa language. The first phase will involve a comprehensive review of the literature to be followed by informal consultation and review of the identified tool (and its items) with women and local experts in Gombe to ensure appropriateness, and

pilot testing (alongside the IDEAS surveys) and refining the adapted tool. Data source in formative phase will come from published and grey literature on RMC in LMIC and pilot data from household surveys, observation of birth, exit interview and birth attendant interview. Data collection and analysis will be performed between November of 2016 and May 2017.

Data collection phase — will involve (a) generating data on prevalence of RMC during facility-based childbirth from household surveys (June July 2017, May-July 2018), observation of birth and exit interviews (June July 2017, November December 2017) — the prevalence of RMC will be assessed in subsequent IDEAS household surveys, observation of births, birth attendant interviews and exit interviews to update indicators of RMC in the results framework; (b) in-depth interviews and focus group discussions (FDG), the qualitative studies will seek to explore women experience from their recent facility-based birth (i.e. women-health worker interaction & condition of place of delivery) in Gombe, identify the attributes and attribute levels and generate items for the choice experiment: 3) conduct the choice experiments at follow-up (at home) 6-months later in November December 2017.

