5.2.1 Observation of births

Sample – this is nested within the facility survey in a sub-set of the 10 highest volume primary facilities within the intervention area facility sample. Using data on volume of births in each of the 57 priority facilities, facilities were ranked from highest to lowest number of births in the six months prior to survey and the top ten selected. In each of these ten facilities, and alongside the facility survey, two medically trained observers are posted in shifts covering day and night deliveries, 7 days a week (for approximately 3 weeks, determined by volume of births and time taken to recruit a sample of 320 births (see IDEAS Gombe data collection protocol for further details)). During working shifts these observers identify and observe women during labour and childbirth using a checklist to

document indicators of clinical and respectful care provided by birth attendants. Data collectors will be well trained to maximise the reliability of assessment.

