5.2.2 Exit interviews with observed women

Sample – each woman whose birth was observed (target recruitment of 320 women) is invited to interview as she leaves the facility. Women are asked a set of questions about the clinical and respectful care they received during labour and childbirth. Data collectors will be well trained to maximise reliability of assessment.

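### Prevalence and change of respectful care taken from openly observed births: allow for staff reacting to observers, and report the figure as care under observation

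*Protocol*

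**What the plan says.** Section 1.2 of the protocol answers its first research question by two routes. One is mothers' reports in the household survey. The other counts how often interactions or facility conditions "are deem (by general consensus) to be humiliating or undignified, through observation of births". The same section expects that "changes in frequency or prevalence of these dimensions of RMC can be tracked or observed over more than one measurement period". Section 4.2 schedules observation for June-July and November-December 2017 and adds that "the prevalence of RMC will be assessed in subsequent IDEAS household surveys, observation of births, birth attendant interviews and exit interviews to update indicators" in the results framework.

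Section 5.2.1 describes the measurement. In each of the ten highest-volume primary facilities of the intervention area, "two medically trained observers are posted in shifts covering day and night deliveries, 7 days a week". A round runs for some three weeks, until the target of 320 births is reached. The observers use a checklist covering clinical and respectful care. The only safeguard stated there is that "Data collectors will be well trained to maximise the reliability of assessment".

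Table 5 lists time of delivery and, for observed births, day of the week. It lists neither days since the observers arrived nor survey round. Table 2 links observation of births to Objectives 2, 4 and 5, and Table 4 gives the household survey as the only source for Objective 1. Neither table assigns observation to the prevalence objective.

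**The concern.** Several items in the Table 1 typology are things a member of staff can choose not to do in front of a stranger with a checklist: rude language, threats, blaming, slapping, restraint. Training observers to record reliably makes two observers agree on what happened. It does nothing about what staff do because an observer is there.

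Two conclusions are at stake. The first is the level: mistreatment on behavioural items is probably under-recorded, so RMC on those items looks better than in unobserved births. The second is change. If staff get used to observers, measured RMC falls with no true deterioration, or a real improvement is hidden. If staff learn what the checklist scores, measured RMC rises with no true improvement. Section 5.2.1 observes intervention-area facilities only, so no concurrent comparison group is available to separate these effects from real change.

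**Working it through.** **The plan's own figure.** The protocol gives no precision calculation for the observed prevalence. Its only prevalence sample size is for the household survey (section 5.1): 1.96² × 0.25 / 0.05² = 384.1, rounded up to 385; 385 × 1.4 × 1.10 = 592.9, so 593. This reproduces and is not in dispute.

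**Inputs from the protocol.** 320 observed births (sections 5.2.1 and 5.2.2); about three weeks, taken as 21 days (section 5.2.1); design effect 1.4 (section 5.1, borrowed from the household survey because none is given for the ten facilities).

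**Assumptions.** Prevalence 50%, births spread evenly over the three weeks, and reactivity of 3 to 15 points. The protocol contains no figure for reactivity, so what follows illustrates consequences and does not estimate the bias.

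1. *Sampling half-width.* 1.96 × √(0.25/320) = 5.5 points; with design effect 1.4, 1.96 × √(1.4 × 0.25/320) = 6.5 points.

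2. *Bias in the level.* If RMC is 5 to 15 points higher in week one only, the three-week figure is raised by 1/3 × 5 = 1.7 to 1/3 × 15 = 5.0 points. If the effect lasts throughout, all 5 to 15 points remain.

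3. *The same on a Table 3 item.* Suppose being watched turns a share r of otherwise disrespectful births into respectful ones. Then unobserved = (observed − r)/(1 − r). For the 55% listened to and supported, r = 0.05, 0.10 and 0.20 give 52.6%, 50.0% and 43.8%.

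4. *Confidence interval coverage.* With design effect 1.4 the standard error is √(1.4 × 0.25/320) = 3.31 points. Coverage under bias b is Φ(1.96 − b/SE) − Φ(−1.96 − b/SE). For b = 3, 5 and 10 points this is about 85%, 67% and 14%, not 95%.

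5. *False change between rounds.* Take two rounds of 320, no true change, and reactivity falling by h. The chance of a two-sided p < 0.05 comes from the usual two-proportion normal approximation with 320/1.4 = 229 births per round. For h = 5 points: null SE 4.67, alternative SE 4.67, Φ((5 − 1.96 × 4.67)/4.67) = about 19%. For h = 3, 10 and 15 it is about 9%, 58% and 90%, against a nominal 5%.

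6. *Would dropping early births help?* Leaving out five days keeps 320 × 16/21 = 244 births, half-width 1.96 × √(0.25/244) = 6.3 points. If the effect lasts one week, 2 of the 16 remaining days are still affected, so residual bias is 2/16 × 5 = 0.6 to 2/16 × 15 = 1.9 points. Before clustering, the root mean squared error moves as follows:
   - 5-point effect: √(1.67² + 2.80²) = 3.25 with all births; √(0.63² + 3.20²) = 3.26 without the first days.
   - 15-point effect: √(5.0² + 2.80²) = 5.7 with all births; √(1.88² + 3.20²) = 3.7 without.

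Dropping early births gains nothing at the low end and helps at the high end. That supports a sensitivity analysis and does not support a compulsory exclusion.

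**The case against.** The strongest reply is that the protocol places prevalence elsewhere. Section 5.1 and Table 4 assign Objective 1 to the household survey, and Table 2 does not link observation to it. Observed frequencies then appear only as descriptive statistics under Objective 2. This is a fair account of the tables, but sections 1.2 and 4.2 state the prevalence and tracking uses in plain terms. The passages conflict and need reconciling; the stated uses do not disappear.

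Second, section 5.2.1 refers to a separate IDEAS data collection protocol, which is not at hand and may contain observer procedures or a settling-in period. That stands: one can say that this protocol states no allowance, not that none exists.

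Third, several stronger readings are tempting and go beyond the text:

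- *Staff know they are being assessed, by two observers at once around the clock, and all births from day one are pooled.* The protocol says two observers are posted in shifts and describes no concealment. Staff awareness is a reasonable inference. Simultaneous presence and pooling from day one are not stated.
- *The effect can be neither seen nor reduced.* Table 5 lists potential confounders and does not limit the analysis. Birth dates should be available, so a display by week is possible; it is simply not planned.
- *The observed figure is an upper bound for RMC.* Many Table 1 items (facility condition, staffing, supplies) cannot readily be changed by a watching observer. Choosing the ten busiest intervention-area facilities may also move a state-level figure in either direction.
- *The direction of false change is known.* Habituation and learning the checklist pull opposite ways, and the protocol does not say the same ten facilities recur. Table 3 shows that births were already observed in ten primary facilities in March 2017, which would weaken a first-arrival effect if these overlap.

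**Conclusion.** The concern holds for behavioural RMC items, in the two uses that sections 1.2 and 4.2 give to observed births: a prevalence and a tracked indicator. The expected direction for the level is too favourable. The size cannot be derived from the protocol; the 1.7 to 5.0 points (or 5 to 15 if the effect persists) rests wholly on an assumed range. A reaction of that order would matter, because it is comparable with the 5.5-point half-width and would raise the false-change rate well above 5%.

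Structural items are much less exposed. So is Objective 2, because observation and the woman's report concern the same watched birth. This is a matter that should be addressed, at little cost; it does not invalidate the study.

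**What to change.** 1. Add days since the observers arrived at the facility, and survey round, to the Table 5 variables for observed births.
2. Show the behavioural RMC indicators by week of observation and by round. A trend within a round would reveal fading reactivity. A flat trend would not exclude a constant effect, which is why item 4 is needed whatever this shows.
3. Keep all observed births in the main estimate and in Objective 2. Add one sensitivity estimate without the first days at each facility, for example five days, leaving about 244 births and widening the half-width from 5.5 to 6.3 points before clustering.
4. Report the result as prevalence of RMC under observation in the ten highest-volume intervention-area facilities, not as the Gombe State prevalence and not as an upper bound. Interpret change between rounds with the same caution.
5. Reconcile section 1.2 with Tables 2 and 4 on whether observation contributes to Objective 1.

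The cost is a little extra analysis and a more cautious label. No new data collection should be needed: Table 5 already records day of the week and follow-up is timed from the birth, so birth dates should be held. The date observers started at each facility should be recorded if it is not already.

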5.2.3 Household follow-up with observed women

Sample – each woman whose birth was observed and was interviewed after discharge before exit will be asked for her consent for a follow-up interview at home six months later. At follow-up, women will be asked the same set of questions and same choice experiment as in the exit interview. Data from the choice experiment at follow-up will be compared with data on choice experiment from the exit interview to assess the stability of derived utilities from time-1(t0-month) and time-2 (t6-months). Data collectors will be well trained to maximise reliability of assessment.

Sample size for validity testing of exit interview and household follow-up interview responses compared to the gold standard observations. To analyse the agreement between observed and reported RMC behaviours we will calculate sensitivity and specificity of reported to observed. This statistical approach does not test a specific hypothesis, but focuses on the width of the confidence intervals around agreement when interpreting results: the larger the number of follow-up interviews we are able to achieve the more narrow the confidence intervals will be.

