this design heterogeneity could be confounded in case of taste heterogeneity and scale differences.¹ Table 3 describe the steps involved.

Table 6. Steps and activities involved

Steps	Activities
Identifying attributes	Identify dimensions or attributes of RMC through qualitative research involving (1) review of published and grey literature and (2) focus group discussion with the target population to augment the secondary data. Example of attributes of RMC includes physical abuse, non-consented care, non-confidential care, non-dignified care.
Assigning attribute levels	Use information generated from qualitative methods above to assign attribute levels. Attribute levels will reflect the range of RMC situations that mothers are likely to experience, e.g. attribute levels for non-dignified care: harsh tone; harsh language; unkind expression. To aid cognition each attribute will have not more than three levels.
Generating the choice sets	Use conjoint Sawthooth software to generate attribute level combination to create hypothetical scenarios — create choice sets. To obtain orthogonal and balance design fractional factorial design will be used.
Pre-testing the questionnaire and data collection	Pre-test, evaluate the process and revise the survey. Use trained fieldworkers to administer the questionnaire to respondents.
Analysing of DCE data	Generate individual level estimates of the part-worth of each mother's utility function. Determine the value associated with each dimension of RMC. Perform segmentation/sub-group analysis based on mother's sociodemographic characteristics.

Sample – the choice experiment will be administered during home follow-up interviews: during follow-up at home in November December 2017 to the same post-partum women with live birth that were observed during childbirth and interview at exit in July 2017.

Sample size – For the choice-based experiment, suggestion of sample size determination by Johnson and Orme will be used, which suggests that the sample size required for the main effects depends on the number of choice tasks (t), the number of alternatives (a), and the largest number of levels for any of the attributes (c) according to the following equation: N>500c/(t×a),⁷ if t =15 (i.e. 15 choice tasks) and a =2 (i.e. # of alternatives) and c =6 (i.e. largest # of levels), then the required sample size =500x6 \div 15x2 =100.

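### The home follow-up that tests recall is defined as 6-12 months after birth, but its only stated dates put it about 3-7 months after birth

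*Protocol*

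**What the plan says.** The protocol describes the timing of the home follow-up of observed women in several places.

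- **Section 1.2, research question 2:** reports are compared with observation at exit and again "during household-follow interview with observed women 6-12 months after birth to test the validity of self-reporting".
- **Section 1.2, research question 3:** the choice experiment is "integrated within the household follow-up interviews (6-12 month post-delivery", the same range for the same visit.
- **Section 5.2.3:** each observed and exit-interviewed woman is "asked for her consent for a follow-up interview at home six months later". At that visit "women will be asked the same set of questions and same choice experiment as in the exit interview". No calendar date is given.
- **Section 4.2:** the data collection phase lists "observation of birth and exit interviews (June July 2017, November December 2017", and the plan is to "conduct the choice experiments at follow-up (at home) 6-months later in November December 2017".
- **Section 5.3.3, under Sample:** the November-December 2017 home follow-up goes to the women "observed during childbirth and interview at exit in July 2017".

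The definition is thus 6-12 months in one section and six months in another, while the only calendar dates for the visit are in November-December 2017.

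**The concern.** Objective 2 asks whether women's own reports of respectful care agree with what was observed. For the home visit, the time since birth is the condition under which agreement is measured, so it belongs to the result. Sensitivity and specificity measured at about five months answer a different question from the same quantities measured at 6-12 months. If the field team keeps to the stated dates and the report keeps to the stated definition, the follow-up validity result will carry the wrong recall length. Both the interval and the dates are fixed in the protocol, so an analysis plan could not resolve the conflict or create interviews at 7-12 months.

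**Working it through.** **Inputs**

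- Births and exit interviews: 1 June to 31 July 2017 (section 4.2), or July 2017 only (section 5.3.3).
- Home visit: 1 November to 31 December 2017 (sections 4.2 and 5.3.3).
- One visit for the recall questions and the choice experiment (sections 1.2 and 5.2.3). This is the step that carries the dates over to Objective 2.
- The few days between birth and exit are ignored. One month is taken as 365.25/12 = 30.4375 days.

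**Interval implied by the dates**

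Shortest = first visit day minus last birth day. Longest = last visit day minus first birth day.

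| Births followed | Shortest | Longest |
|---|---|---|
| June-July | 31 Jul to 1 Nov = 93 days (3.1 months) | 1 Jun to 31 Dec = 213 days (7.0 months) |
| July only | 93 days (3.1 months) | 1 Jul to 31 Dec = 183 days (6.0 months) |
| June only | 30 Jun to 1 Nov = 124 days (4.1 months) | 213 days (7.0 months) |

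The midpoints of the June-July and November-December windows are 1 July and 1 December. They lie 153 days apart, which gives a mean of 153/30.4375 = 5.0 months. For July births only, the midpoint is 16 July and the mean is 138/30.4375 = 4.5 months. The stated six months is therefore not reproduced as an average on either reading.

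**Share reaching six calendar months, with births and visits spread evenly (an assumption)**

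- A birth on day k of June reaches six months on day k of December, leaving 32 - k eligible visit days. Summed over k = 1 to 30, this is 31 + 30 + ... + 2 = 495 birth/visit pairs.
- A birth in July reaches six months on 1 January 2018 at the earliest, so it contributes no pairs.
- June-July births: 495/(61 × 61) = 495/3721 = 13%.
- July births only: 0%.
- June births only: 495/(30 × 61) = 495/1830 = 27%.

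Section 5.2.1 expects recruitment to take about three weeks, so births may be bunched. If they all fell on 1-21 June, the eligible pairs would be 31 + ... + 11 = 441, and the share 441/(21 × 61) = 441/1281 = 34%. The share depends on the spread. The 7.0-month ceiling does not.

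**Dates that the stated window would need**

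For births from 1 June to 31 July 2017, the six-month dates run from 1 December 2017 to 31 January 2018. The twelve-month dates run from 1 June to 31 July 2018. The dated visits overlap the 6-12 month window only between 6 and 7 months, and only for June births seen in December.

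**The case against.** Four points can be made for the protocol.

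1. **The dates belong to the choice experiment.** Section 5.2.3, which governs the recall interview, gives no date and ties the visit to the woman. This is true, and applying the 2017 dates to Objective 2 is an inference. It is a firm one, because section 5.2.3 gives both instruments at one visit and section 1.2 places the choice experiment inside that visit.
2. **Part of the window is reached.** A reader might infer that recall at 6-12 months is not tested at all. The documents do not support that: every June birth reaches six months by 30 December, so June births seen in December fall at 6-7 months. The stronger reading needs July births only, as in section 5.3.3.
3. **There is a second observation round.** Section 4.2 also lists births observed in November-December 2017. Under section 5.2.3, their follow-up would fall at about 1 May to 30 June 2018. The protocol dates no such follow-up, and at six months it would reach only the lower edge of the window. The quarter marks in Table 2 could not be read in the text available, so they neither settle nor worsen the matter.
4. **The wider harm is not documented.** A reader might compare the 7-month maximum with the household survey's 24-month look-back and conclude that (24 - 7)/24 = 71% of births, if evenly spread, lie beyond the tested recall. That does not measure this conflict: an exact six-month visit gives 18/24 = 75%, and a full twelve months still leaves 12/24 = 50%. A reader might also infer that shorter recall flatters sensitivity and specificity. The protocol gives no figure for loss of accuracy over time, so the size of any such effect is unknown.

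The first three points narrow the finding without removing the conflict. The fourth removes two arguments that should not be used. In addition, no sample size depends on the interval, and the exit-interview comparison is unaffected.

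**Conclusion.** The point holds as an internal inconsistency to be reconciled, not as a failure of the design. On the stated dates the home visit falls about 3.1-7.0 months after birth, mostly under six months, or 3.1-6.0 months if only July births are followed. Validity over 6-12 months is largely untested, and no dated follow-up covers recall beyond 7 months. The range rests on the calendar windows in sections 4.2 and 5.3.3 and on the recall questions sharing the choice-experiment visit. The 13% rests further on an even spread of births and visits, which the protocol does not state.

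**What to change.** Reconcile section 1.2 (research questions 2 and 3) with sections 4.2, 5.2.3 and 5.3.3, and state whether the followed cohort is June-July or July 2017 births. Then choose one of two routes.

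- **Keep 6-12 months.** Set each visit from the woman's own delivery date so that it falls between her six-month and twelve-month dates, as worked out above, and replace the November-December 2017 window. The cost is moved field weeks and possibly slightly more loss to follow-up.
- **Keep November-December 2017.** Restate the interval as about 3-7 months (3-6 if only July births are followed) in every place, and limit the follow-up validity conclusion to that recall length. The cost is wording only.

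On either route, report the actual time since birth alongside the follow-up sensitivity and specificity. Also say whether the November-December 2017 observation round will be followed up at home and, if so, when.
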